- Compare monthly RDT consumption data and volumes/TPRs reported via the registers and HMIS/DHIS2 with manual counts of used RDTs and RDT positives collected from health facilities and CHWs in monthly counts. A digital tool will be used alongside the manual counting process to take pictures of each RDT counted and provide the RDT test result.
- Identify discrepancies between reported and manual RDT counts, TPRs and ACT consumption and discuss these in monthly validation meetings.
- Observe whether discrepancies will disappear over time:

⁸ Cameroon National Malaria Control Program annual report, 2022.

⁹ Cameroon DHIS2, 2022

- Manually and digitally counted RDT volumes and positives converge with what is reported in registers/DHIS2
- Manually and digitally country RDTs and RDT positives will converge with reported RDT and ACT consumption volumes
- Assess operational feasibility, costs, and acceptability of the manual RDT storage and count method.

Participating health care workers and CHWs in study sites will be informed about the manual count and asked to store all used RDTs in labeled storage containers that will be provided for this purpose. HCW/CHW are expected to conduct business as usual, interpreting and reporting RDTs per national guidelines and recording the RDT results. At the end of each month, supervisors will collect and count the RDTs. The number of positive and total RDTs will be manually recorded and totals will be compared with the register and DHIS2 reported RDT country and positives.

Primary outcome:

• The primary outcome will be a comparison of the volume and test positivity rate (TPR) from the manual counts by trained supervisors to the TPR recorded in the HMIS (historic, surrounding areas, by CHWs and HF) on a monthly basis over the course of the 6-month intervention.

Secondary:

The secondary outcomes of this study are to:

- 1. Compare the manually counted RDTs and RDT positives to what was recorded in the registers
- 2. Compare the manually counted RDTs and RDT positives to the consumption of RDTs and ACTs recorded in the DHIS2 and pharmacy records (i.e., supply log)
- 3. Compare the costs of implementing the monthly RDT validation with potential savings from reductions in prescription of ACTs
- 4. Measure the impact of monthly RDT validation exercises on changes in HCWs' subjective norms, attitudes, perceptions and practices related to RDTs

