- 5. Measure the acceptability and feasibility of conducting monthly RDT validation exercises among stakeholders involved

LITERATURE REVIEW

1. Introduction

Malaria remains a major public health burden in Cameroon, contributing to high morbidity and mortality, particularly among children under five and pregnant women. In response to this challenge, parasite-based diagnosis is the standard recommendation by the WHO for testing before malaria treatment¹⁰. While RDTs have improved access to malaria diagnosis, concerns over accuracy, test interpretation, and data reliability persist. These concerns are as equally expressed for health facilities as CHW settings, where reported malaria test positivity rates are high.

Inconsistent RDT interpretation and errors in manual test recording have been well-documented in sub-Saharan Africa¹¹. The introduction of a simple method to count collected RDTs and interpret their results to verify reported test, case and consumption data provides an opportunity to explore whether malaria surveillance data, malaria case management and supply chain practices can be improved in Cameroon.

2. Challenges in Malaria Diagnosis and Data Quality

The effectiveness of malaria RDTs depends on the correct interpretation of and compliance to the test result. Numerous studies have shown that health workers often may not conduct the RDT according to the manufacturer's instructions and/or misinterpret the test results, leading to false-positive or false-negative diagnoses¹². According to Cunningham et al, the most common sources of errors include: (i) Failure to adhere to the correct RDT reading time as specified by manufacturers, leading to result inaccuracies and (ii) Misclassifying faint test lines as negative due to inconsistent lighting conditions or inadequate training.

A study conducted in Uganda found that misinterpretation of RDTs by health workers led to overdiagnosis in 21% of cases, contributing to unnecessary antimalarial use¹³. Another study by Maltha et al revealed that errors in RDT use by end-users were common and related to procedural mistakes, safety issues, and result interpretation¹⁴. These included delayed

¹⁰ WHO. (2012). Guidelines for malaria. Geneva: WHO

¹¹ Maltha, J., Gillet, P., & Jacobs, J. (2010). Accuracy of malaria rapid diagnostic tests. Malaria Journal, 9(1), 113.; Mukadi et al., 2014

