All health workers (n=32 - 2 per HF) and CHWs (n=31) in the Garoua Boulai health district will be approached for consent and included in the study. We anticipate collecting a minimum of 2121 tests conducted during the study period in outpatients and 1292 tests conducted in the community by polyvalent CHWs.

Inclusion/Exclusion Criteria

PARTICIPANTS- health workers in participating health facilities and CHWs in health areas (catchment) tasked to conduct the malaria RDT in patients suspected of having malaria

INCLUSION CRITERIA:

- All RDTs conducted in outpatients suspected of having malaria by participating CHWs in the targeted health area
- All RDTs conducted by participating healthcare workers on patients at the HFs
- All healthcare workers and community health workers that provided consent to participate in the study

EXCLUSION CRITERIA:

- RDTs conducted by CHWs on pregnant women (Because tests from pregnant women carried out by CHWs are not recorded in the DHIS2) or in patients
- Nonconsenting HCWs

Study Design

This is an observational pilot conducted over six months in the Garoua-Boulaï Health District. It will involve 16 health facilities and 31 CHWs routinely performing malaria testing. The selected district was selected because (i) historic testing data would suggest we could easily meet the sample size of 2121 tests in a period of 6 months in the HFs, (ii) the research team already has ongoing operations in the district, (iii) CHWs carry out Integrated Community case management (ICCM). In collaboration with district health officials and the nurse in charge of the participating health facilities, the health workers, supervisors and the community health workers in the district that conduct malaria RDTs will be invited to a short training in which the study will be explained. The health workers will be informed of the manual count of the RDTs and equipped with containers for storage of the used RDTs. They will be requested to store the used RDT readers be it positive or negative. Supervisors will collect the stored readers monthly for the manual and digital review and counting. Discrepancies will be communicated back to

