nurses in charge of the participating health facilities after each count. The supervisors and the district health official will participate in the monthly count process, facilitated and chaired by the research team (at least for the first few months). Participants in the counting process will receive brief training on manual RDT result interpretation by the research team and use of the digital tool (a mobile app downloaded on a phone).

Sampling calculation

We hypothesize that the TPR recorded in the registers differs from the TPR found through the manual count and used the anticipated difference in our sample size calculations. We calculated sample size requirements based on a cluster randomized two-sample unpaired t-test for the comparison of two proportions using standard formulae (Hayes and Bennett, 1999). We fixed the Type 1 error at 5% and the power at 80%. Prior to the intervention we assume the TPR to be 65% in HFs and 95% in CHWs. We hypothesize that this, as a result of our intervention, will decrease to 40% in HFs and 50% in CHWs. We accordingly calculated separate sample sizes for HFs and CHWs based on the baseline and expected proportions. Since we will be sampling HFs and CHWs, we expect that there will be clustering effects in the populations that these Point Of Care serve. As such, we took clustering into account by applying a design effect based on the total population (i.e. total number of tests) that these POCs cover over six months (the assumed sampling time period) - using 2023 testing data for all HFs and CHWs in East region. We used an ICC of 0.05. Based on these assumptions and calculations, the maximum sample size required for HFs and CHWs respectively is 2121 and 1292 tests. We aim to sample from 16 HFs and 31 CHWs over a single district in the East region to control unknown confounders and differences in behavior/population between HFs and CHW catchment populations.

Tools for data collection

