Data will be collected through a review of routine health records, one survey and in depth interviews to assess the introduction of the counting on performance, diagnostic accuracy, and stock management outcomes. The routine health records include the registers, which will be filled by health care workers (health facility and CHWs), and the DHIS2, metadata on test results, RDT and ACT consumption data and timestamps for each test. During the data validation meetings, the aggregated results of the manual and digital count and the health records will be recorded and stored in a cloud-based system. For the digital count, we will use a customized Audere 'Healthpulse' Android mobile app on a phone provided by the research. The user is instructed to open the app and prompted to take a picture of the RDT result window. The Audere app is trained to interpret and provide the result of the RDT picture to the end user. The aggregated digital and manual count will be compared and any discrepancies will be reviewed and resolved by the supervisor, the district health official and the research team.

A survey will be conducted among the participating health workers on their perceptions of malaria RDTs. In depth interviews will be conducted with all stakeholders involved in the data

validation meetings to explore feasibility of the validation meetings post study. The research team will also collect data on the financial and human resources required to conduct the RDT counts.

Study Outcome Measures

The primary outcome of the study will be the RDT volume and TPRs obtained from the manual count compared with the RDT counts TPRs recorded in the HMIS, health facility registers, and CHW records. This will provide insights into potential discrepancies in malaria diagnosis and reporting accuracy.

Specific outcomes will include the following:

S/N	Type of Outcomes	Outcome	Methods of measurement
1	Primary	The volume and proportion of RDT results reported as positive	On a monthly basis, RDT counts and RDT positives recorded through the manual count will be compared to RDT count and TPR recorded in the registers (by health facility and CHWs attached to that facility) and what was recorded in the DHS2 for that facility and for the CHWs attached to that facility

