To ensure compliance with study protocols, monthly CHW and health facility supervision visits will be conducted throughout the study period. These visits will serve to verify all used RDTs are stored and labelled appropriately using the designated collection devices, to troubleshoot any issues around RDT storage, to copy (or bring) the registers for the review period, and to transport the cassettes for the count. Informed, written consent will be obtained from all participants involved in the in depth interviews and qualitative survey. Participants will be

informed that their participation is entirely voluntary and that they are under no obligation to participate if they do not wish to. They will be assured that no negative consequences will result from their decision to either participate or decline. They will also be informed that they have the right to withdraw from the study at any point, without facing any repercussions. Confidentiality will be maintained throughout the study.

Since all participants are expected to be literate, written consent will be feasible and preferred. Should any exceptions arise, alternative methods of obtaining consent (such as oral consent witnessed by a third party) will be considered, ensuring the process remains ethical and transparent.

Data collection and SUBJECT CONFIDENTIALITY

Strict measures will be taken to ensure the confidentiality of all data collected during the study. All quantitative data collection activities will be carried out using smartphones equipped with Open Data Kit (ODK) tools and the research team will be trained on the data collection processes. The tools will be implemented using a smartphone which will be provided to all research assistants.

Participant confidentiality will be maintained during the intervention. No patient identifying information will be collected. Results will be reviewed in aggregate by CHWs and health facility Data will be stored in secured registers. The data will only be accessible to the Data Manager and the PI. It will be reviewed regularly to ensure quality and completeness. Only fully deidentified data will be provided to other study personnel or statisticians. Only fully deidentified data will be shared.

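### The supervisors who make the reference count also have access to the registers, and nothing masks the reading of positives or locks it before the reported result is seen

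*Protocol*

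**What the plan says.** The primary outcome, under AIM and Outcomes, sets the volume and test positivity rate (TPR) from "manual counts by trained supervisors" against reported figures. The Study Outcome Measures section adds facility registers and community health worker (CHW) records to the comparison.

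On who counts, AIM and Outcomes states: "At the end of each month, supervisors will collect and count the RDTs". Study Design agrees: "Supervisors will collect the stored readers monthly for the manual and digital review and counting". It also describes a joint session: "The supervisors and the district health official will participate in the monthly count process, facilitated and chaired by the research team", the chairing being assured only for the early months.

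The purposes of the monthly supervision visit, listed under Participant Enrollment and informed consent, include "to copy (or bring) the registers for the review period, and to transport the cassettes for the count".

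Tools for data collection adds a second reading: "The Audere app is trained to interpret and provide the result of the RDT picture to the end user". The aggregated manual and digital counts are then compared, and "any discrepancies will be reviewed and resolved by the supervisor, the district health official and the research team".

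AIM and Outcomes names convergence of the counts with registers and DHIS2 as something to look for. The quantitative analysis plots the ratio of register TPR to cassette TPR over the six months and sets it beside the change in DHIS2 TPR.

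**The concern.** A reference measurement should be made without knowledge of the result it is meant to check. Here the same group handles both. Reading a cassette involves judgement: the literature review lists, among common errors, "Misclassifying faint test lines as negative due to inconsistent lighting conditions or inadequate training". A reader who knows what the facility reported may settle a doubtful line accordingly.

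Two things are at stake. One is the size of the discordance, which is the main estimate. The other is its course over time. Discrepancies go back to the nurses in charge after every count, so from the second month readers know that disagreement has consequences. An influence that changes with month would enter the very trend the study wants to interpret.

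**Working it through.** No figure in the protocol rests on this point, so there is nothing to reproduce. The check is a reading of the workflow, followed by illustrations on stated assumptions.

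**1. Exposure.** The enrollment section does not name who makes the visits. AIM and Outcomes and Study Design both give collection of the cassettes to the supervisors, and the visit that transports the cassettes also copies or brings the registers. So the natural reading is that the register is within the readers' reach before the count.

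**2. Masking.** AIM and Outcomes has the positives and totals recorded and then compared with the register and DHIS2. That orders the comparison, not what the reader has already seen. No section provides for coded containers, closed registers or a locked count. The only SOP mentioned concerns storage of cassettes.

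**3. Size.** The documents give none. Let f be the assumed net share of the gap between reported and true TPR that is lost through unmasked reading:

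counted TPR = true + f × (reported − true)

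The Sampling calculation section assumes 65% falling to 40% in health facilities (HFs) and 95% falling to 50% in CHWs. These are worded as before and after the intervention; here they only stand in for reported and true values.

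| f (assumed) | HF counted | HF gap | CHW counted | CHW gap |
|---|---|---|---|---|
| −10% | 37.5% | 27.5 | 45.5% | 49.5 |
| 0 | 40.0% | 25.0 | 50.0% | 45.0 |
| 10% | 42.5% | 22.5 | 54.5% | 40.5 |
| 25% | 46.25% | 18.75 | 61.25% | 33.75 |
| 50% | 52.5% | 12.5 | 72.5% | 22.5 |

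Example: 40 + 0.25 × 25 = 46.25. The negative row covers a reader who expects over-reporting and errs the other way. In cassettes, f = 10% means a net 0.10 × 25 = 2.5 per 100 in HFs and 0.10 × 45 = 4.5 per 100 in CHWs.

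**4. Can the trend be interpreted?** Take HFs starting at reported 65% and counted 40%, and assume two later months:

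- *A, reporting improves.* True TPR stays at 40%, the reading is unbiased, and reported TPR falls to 60%. Recorded: 60% and 40%.
- *B, reporting does not improve.* True TPR falls by an assumed 5 points to 35% with season. Over-reporting stays at 25 points, so reported TPR is 60%. With f = 20% the count is 35 + 0.20 × 25 = 40%. Recorded: 60% and 40%.

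In both, the gap narrows from 25 to 20 points and the ratio falls from 65/40 = 1.63 to 60/40 = 1.50, with the same fall in reported TPR. The manual count and the ratio cannot tell A from B. An app reading that was accurate and left unadjudicated would: 40% in A, 35% in B.

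**The case against.** The strongest reply has five parts.

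- **Direction.** A reader might infer that the count will drift towards the register and that discordance will be understated. The documents do not support that. They contain no data on it, and since the study was prompted by suspected over-reporting, an alert reader could err the opposite way. The quoted faint-line error is a positive read as negative, so a nudge towards positive could even correct it. This stands: the point is a risk of bias, not a demonstrated drift.
- **Re-reading evidence.** The literature review cites unpublished work in which stored RDTs, re-read by an expert panel, showed few discrepancies from the field reading. This favours low values of f. It shows that readings keep, not that a reading made with the register at hand is unaffected.
- **The app.** It reads a photograph of each cassette and does not use the register. This is a real but partial safeguard. The outcome uses the manual count, the two counts are compared in aggregate so opposite errors can cancel, and people with no stated masking resolve the differences.
- **Separate series.** Reported TPR, DHIS2 and ACT records are also held, and drift alone would raise the count while reported TPR stayed flat. That helps if transmission is steady. Once true TPR moves with season, as in example B, the patterns can coincide.
- **Inference and scope.** The visitor is not named, the count is collective, and a line-list register must be tallied before its total is known. These points reduce the likely exposure without removing it. It is also fair that the fix is operational, but who reads the reference, and knowing what, is a design matter that this protocol has already set out.

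**Conclusion.** The point holds as a gap in the protection of the reference measure. The supervisors who read the cassettes have access to the registers, and the protocol fixes neither masking nor a count-first lock. Readings of positives may be influenced in either direction. If the influence runs towards the register and changes with month, it cannot be cleanly separated from true convergence using the manual count or the register-to-cassette ratio.

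The size is unknown. On the assumed range f = 10% to 50%, the gap would shrink by 2.5 to 12.5 points in HFs and by 4.5 to 22.5 points in CHWs; f = 0 gives no bias. The harm is to the estimate and its trend. RDT volume, the other half of the primary outcome, does not depend on judging lines and is barely affected.

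This rests on supervisors being the ones who make the visits, and on the workflow as the protocol gives it. Any separate SAP or counting SOP was not available.

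**What to change.** State the following in the protocol or the counting SOP:

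1. Register copies stay closed after the visit, for example sealed and held by the research team.
2. For each point of care and month, the manual positives and totals and the unadjudicated app result are entered and locked in the data form.
3. Only then are the register and DHIS2 figures for that month opened.
4. The unadjudicated app TPR is reported beside the manual TPR, by month, including any plot of convergence.

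Coded containers are a low-cost addition where practical. Having supervisors read containers from points of care that they do not supervise is optional: the number of supervisors is not stated, and it would alter the process whose feasibility is being assessed.

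The cost is slightly more handling of documents and a few more minutes at each monthly meeting. If only adjudicated counts are kept, the influence cannot be removed afterwards, so the change should be in place before the first count.

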Malaria remains a leading public health challenge in Cameroon, with diagnostic accuracy and data quality among the key barriers to effective case management⁴. The country relies heavily on rapid diagnostic tests (RDTs), with 69% of patients tested using RDTs in 2023⁵. However, very high Test Positivity Rates (TPRs) and supply chain inefficiencies raise concerns about the accuracy of reported malaria cases in Cameroon⁶: Providers may not interpret the test accurately or may report negative RDTs as positive. This could lead to inflated case counts and incidence which distort trends and contribute to observed lack of progress in reducing malaria burden. In addition, administering these patients antimalarials may not address the true cause of illness which can increase the risk to patients for morbidity and mortality. Finally, irrational ACT use may contribute to stockouts as well as wastage and increased risk of developing antimalaria resistance.

Data from the District Health Information System (DHIS2) show that TPR varies widely across Cameroon, with the Southwest reporting rates as high as 89% among public sector health workers, while some regions reporting in the lower 60% range. The Annual Blood Examination Rate (ABER) is highest in the East, Adamawa and Far North regions, ranging between 15-26% (including active testing). The average TPR among Community Health Workers (CHWs) is 83%, significantly higher than in health facilities, with minimal variation between age groups. While it is plausible that CHWs, as first-line responders, test only febrile patients with a high likelihood of malaria, qualitative data suggest that other factors may be influencing these high positivity rates. Key Informant Interviews (KIIs) with malaria experts in Cameroon conducted by CHAI in 2023 for example indicate that financial incentives tied to reporting positive cases could be a factor, leading to potential overreporting of malaria cases⁷.

The high TPR has led to questions around the accuracy of reporting the test results by health worker (HW) and community health workers (CHW). Previous efforts in other low- and middle-income countries have shown discrepancies between reported and 'true' TPRs (i.e., using

¹ WHO Malaria Guidelines 2023

² A review of the WHO malaria rapid diagnostic test product testing program (2008–2018): performance, procurement and policy. Jane Cunningham, 2019.

³ World Malaria Report, WHO, 2024.

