In Depth Interviews with participants will be conducted in designated private spaces. If a private space is not available, an alternate location will be used to maintain confidentiality. Interviews will be audio recorded, transcribed verbatim in English language. Personal identifiers such as names and phone numbers will only be collected during the informed consent process and will not be recorded during interviews. The names of health facilities will be collected during data collection for identification purposes but will be excluded during data cleaning to ensure confidentiality.

To minimize risk of disclosure to others and discrimination or stigmatization, measures will be taken to avoid loss of confidentiality. A unique identification number will be assigned to all participants. Access to the completed study instruments and databases will be limited to the project manager, project lead, and data analysts. All data files will be password - protected.

Data analysis

1. Quantitative analysis

The primary outcome will be assessed with a chi-squared test to analyze whether the difference between reported TPR and counted TPR is significantly significant. This will include outcomes for an average across all surveyed points of care (POCs), disaggregated by HFs and CHWs, and compared between baseline (pre-intervention) and endline (after six months of the intervention).

We will further investigate the difference and change in TPR by constructing a mixed effects linear regression model with the POC-month as the unit of analysis and TPR as the outcome variable. The model will include a binary indicator to exhibit pre/post intervention (implementation of the RDT check), a binary variable to indicate intervention group (i.e. "reported" or "counted" TPR), a dummy variable to exhibit month since introduction of the intervention, and a random effect variable for POC type to account for clustering. 95% confidence intervals will be fit around the TPR per POC-month.

To determine whether changes in TPR were due to changes in provider behavior or changes to the DHIS2 data, the ratio of TPRs from the health facility register to the RDT cassettes will be plotted over the six months of the intervention and compared to the change in TPR reported from the DHIS2 data.

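### The primary outcome is RDT volume and TPR, but every analysis stated for it uses TPR alone, so excess reported tests and cases in about the counted proportion would not show.

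*Protocol*

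**What the plan says.** **Outcome definition.** Under AIM and Outcomes: "The primary outcome will be a comparison of the volume and test positivity rate (TPR) from the manual counts by trained supervisors", set against the HMIS each month. Study Outcome Measures repeats both components in its text ("The primary outcome of the study will be the RDT volume and TPRs obtained from the manual count") and in the first row of its table ("The volume and proportion of RDT results reported as positive"). AIM and Outcomes also lists, among the things to be observed over time, "Manually and digitally counted RDT volumes and positives converge with what is reported in registers/DHIS2".

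**Analysis.** Data analysis, Quantitative analysis, states: "The primary outcome will be assessed with a chi-squared test to analyze whether the difference between reported TPR and counted TPR" is significant. The mixed-effects model is then specified "with the POC-month as the unit of analysis and TPR as the outcome variable". The third analysis plots a ratio of TPRs, register over cassettes, and sets it beside the change in DHIS2 TPR. None of the three uses the number of tests or the number of positives as an outcome. The hypothesis in Sampling calculation also concerns TPR only.

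**Motivation.** The opening background text says of misread or misreported tests: "This could lead to inflated case counts and incidence which distort trends". The evidence cited from Benin is an annual reduction of 20-25% in cases and ACT consumption.

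**The concern.** Two parts of the current text disagree about what the primary outcome is. This goes beyond detail that a statistical analysis plan would fill in, because the Data analysis section positively assigns a TPR test to the primary outcome and leaves volume without a method.

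The omission matters because TPR is a ratio. It is blind to any difference between reported and counted data that scales tests and positives alike, such as register entries for tests not done that carry the usual share of positives. The stated harm (inflated case counts) and the cited benefit (fewer cases, fewer ACTs) are both quantities of cases. A primary test showing agreement, or TPR converging over six months, could therefore coexist with a persisting excess of reported cases. If the choice between the components is left open, it may also be made after the results are known.

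**Working it through.** **Inputs from the protocol.** Sampling calculation gives 2121 tests for health facilities (HFs) and 1292 for CHWs, expected TPRs of 40% (HF) and 50% (CHW), and assumed pre-intervention TPRs of 65% (HF) and 95% (CHW). The protocol states no figure for a volume difference, so there is none to reproduce. The inflation scenarios below are assumptions.

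**Why TPR can be blind.** Let n tests and x positives be counted, and let x₀ = x/n. If the reports contain a further a tests of which a share q is positive, reported TPR = (x + qa)/(n + a). This equals x₀ for every a when q = x₀, and exceeds it only as far as q exceeds x₀.

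**Test used.** Pearson chi-squared without continuity correction, counted against reported, applied as the plan describes it.

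*Excess in the same proportion (q = x₀)*
- HF, +25%: counted 848/2121 = 40.0%. Reported tests 2121 × 1.25 ≈ 2651, positives 848 × 1.25 = 1060, TPR 40.0%. Chi-squared = 7 × 10⁻⁶, p = 0.998. Excess positives: 1060 − 848 = 212. Excess tests: 2651 − 2121 = 530.
- HF, +50%: 848/2121 against 1273/3182, p = 0.985, 425 excess positives.
- CHW, +25%: 646/1292 against 808/1615, p = 0.987, 162 excess positives.

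*Excess richer in positives than the counted tests (HF, 530 added tests)*
- q = 0.50: TPR 42.0%, p = 0.16.
- q = 0.65: TPR 45.0%, p = 0.0005.
- q = 1: 1378/2651 = 52.0%, p = 1.5 × 10⁻¹⁶.
- A smaller all-positive excess of 212 tests (10%): 1060/2333 = 45.4%, p = 0.0002.

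*Negatives recoded as positive, volume unchanged (HF, 40% to 65%)*
- 848/2121 against 1379/2121: chi-squared = 266.5, p = 6 × 10⁻⁶⁰.

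*True TPR near the ceiling (1292 tests, 323 added, all positive)*
- Counted 1227/1292 = 95.0%, reported 1550/1615 = 96.0%, p = 0.19, with 323 excess positives. The 95% is the protocol's assumed pre-intervention CHW rate; using it as a counted TPR is an assumption.

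*Negative cassettes not stored (assumption)*
- An HF reports 1379/2121 = 65% when the truth is 848/2121 = 40%, and 816 negative cassettes are missing. The count is 848/(2121 − 816) = 848/1305 = 65%, p = 0.98. Here 1379 − 848 = 531 reported positives have no positive cassette, and only the volume ratio, 2121/1305 = 1.63, signals a problem.

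**Link to Benin.** An excess of 25% over the true count, once removed, is a fall of 0.25/1.25 = 20% in reported cases. A 25% fall would need reports 1/0.75 = 1.33 times the truth. The 25% illustration therefore matches the lower end of the 20-25% range.

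**The case against.** The strongest reply is that the planned test fits the mechanism the protocol names. The background text speaks of providers misreading tests or reporting negatives as positive, and of incentives tied to positive cases. Both raise TPR, and the calculations show that the test detects recoding, and added positives at HF level, very clearly. The aim and the sample-size hypothesis are also framed as TPR discordance. That stands, and it limits the point: the documents do not suggest that proportional inflation is expected.

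A reader might infer that the trial ignores volume, or would give a wrong answer on reporting accuracy and ACT need. The documents do not support this. The outcome table has RDT counts compared monthly, the first two secondary outcomes compare counted tests and positives with registers and with RDT and ACT consumption, and another table row compares positive cassettes with ACTs administered. An excess of 212 cases could be seen there. What is missing is a stated method for volume within the primary analysis.

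A reader might also take the Benin result as showing that cases fall while TPR does not. The protocol does not report what TPR did in Benin.

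Finally, a volume ratio has its own weakness. Potential Risks names loss or damage of cassettes, which raises the ratio without any over-reporting, whereas TPR is unaffected if loss is unrelated to the result. That argues against a pass/fail rule on volume, but not against analysing it.

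**Conclusion.** The contradiction is real. Volume is a declared component of the primary outcome in AIM and Outcomes and in Study Outcome Measures, and no analysis stated for the primary outcome uses it.

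The consequence is conditional. The stated primary test can show agreement while reported cases exceed positive cassettes if the excess is close to proportional, if true TPR is near 95%, or if negative cassettes are selectively not stored. In the illustration, p = 0.998 goes with 212 unmatched positives out of 1060 reported (20%). This rests on an assumed 25% proportional excess at the planned HF size. Outside those conditions TPR does respond.

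Nothing is irrecoverable, since both totals are collected, but the two sections should be reconciled before data are examined.

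**What to change.** Preferred: in Data analysis, Quantitative analysis, add for each POC-month the ratio of reported to counted total RDTs and the ratio of reported to counted positive RDTs. Give overall estimates for HFs and CHWs with intervals that allow for clustering by POC, for example from a count model with a term for data source or from a cluster bootstrap. Report them beside the TPR difference. State that they are interpreted together with what is known about cassette loss, because loss also raises both ratios. Do not impose a joint pass/fail rule.

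Alternative: make TPR the sole primary outcome in AIM and Outcomes and in Study Outcome Measures, and list volume as a secondary outcome with a stated analysis.

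Cost: wording and modest extra analysis. Both totals are already recorded at the monthly counts, so no new data collection is needed.
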